1.3.4 Need to assign patients with regard to prior purine analog

Based on CR rates of 91 and 62% for cladribine in patients with 0 and 1 prior courses of cladribine, respectively [8], response in this trial, including MRD endpoints, may likely be related to whether or not patients received prior cladribine or the other purine analog pentostatin. Therefore, patients need to be separated into two groups prior to randomization. This trial may result in a recommendation that cladribine + rituximab become the standard treatment only for newly diagnosed HCL, or only for HCL with 1 prior cladribine or pentostatin course, or for both groups, or for neither. Prospective randomization should facilitate the validity of such recommendations.

1.3.6 Randomization ‘up front’ and assessment of MRD response at 6 months

The existing trial at MD Anderson, which employs rituximab 4 weeks after starting cladribine, allows assessment of MRD in all patients 1 month after cladribine alone, an important endpoint. However, beginning cladribine and rituximab together is more consistent with the literature regarding combined cladribine and rituximab in CLL and HCL [53, 54]. Combined treatment would also allow for synergism between the 2 agents. Also, it has been shown that while 2 or 3 months is insufficient, 6 months is enough time to judge bone marrow response to cladribine in HCL [11, 59, 61]. It would be very unlikely that patients receiving cladribine alone would need additional treatment before 6 months after cladribine. Thus, this protocol will allow 6 months to judge response after either cladribine or cladribine + rituximab, but, like the MD Anderson study, will also check for MRD by all tests at the 1 month time point.

1.3.7 Avoiding bone marrow biopsy (BMBx) in HCL

BMBx has always been the key test used to determine if HCL patients with hematologic recovery after treatment have achieved a CR. However, it is painful for patients and many physicians avoid BMBx in managing HCL. We found flow cytometry of the blood to be more sensitive than

immunohistochemistry of the BMBx in detecting HCL, since 5% vs. 11% of patients in CR after BL22 had MRD by these methods, respectively [38]. Secondly, success of treatment may be estimated by hematologic recovery and decrease in circulating HCL cells by flow cytometry, although without BMBx it cannot be determined whether patients had CR or PR. Finally, patients in CR or PR after treatment are generally followed without BMBx and not retreated until cytopenias or other indications for treatment (detailed in Section 2.1.1.3) develop. We believe that even without BMBx, new tumor markers and flow cytometry techniques, together with CBC results, could be used with acceptable accuracy to predict whether patients have CR. More importantly, the status of tumor markers and MRD studies may be more important than BMBx in predicting how long a response will last. Finally, to correlate bone marrow MRI signal with bone marrow biopsy, patients will obtain cervical and thoracic spine MRI at baseline and at bone marrow restaging time points, when feasible. The MRI signal in HCL is abnormal at baseline, remains abnormal immediately after achievement of completely remission due to enhance production of normal blood cells, and eventually becomes more normal. A secondary research objective is to define this correlation in a large number of patients and time points, and to determine when after achievement of CR the MRI normalizes. If the correlation is strong, an MRI may be useful in the future to determine if patients might be relapsing or in long term CR. Thus, an important goal of this study is to prospectively correlate BMBx results to other less invasive tests of tumor burden and MRD; and to allow better management of HCL without BMBx.

1.3.8 Ability to recruit HCL patients for the trial

This trial requires recruiting samples from 155 HCL and 20 HCLv patients. The Clinical Immunotherapy Section of the Laboratory of Molecular Biology (LMB) has prescreened a total of 217 patients with HCL, 77 in the past 3 years. Although we did not request patients with 0-1 prior courses of cladribine, 5 (6%) patients had 0 and 15 (19%) had 1 prior courses of cladribine and likely would have been eligible. Patients eligible for this trial would not be eligible for HA22 or BL22, since those trials require at least 2 prior therapies. Those 2 therapies would either be 2 courses of purine analog or a course of purine analog and 1 of either rituximab or another purine analog. Thus, this trial will not conflict with other active NIH HCL trials 06-c-0150 using LMB-2 and 07-c-0130 using HA22. We believe it will be feasible to recruit all the patients using NIH as a single site. At a November 2007 international meeting of HCL experts, it was recognized that standard therapy for HCL has remained unchanged for nearly 20 years and that the optimal role of rituximab in HCL management needs to be determined with a randomized trial. We believe that these and other investigators will be able to contribute significantly to this trial by sending samples and/or treating patients.

1.3.9 Following tumor markers in HCL patients

We have developed several novel assays quantifying tumor burden in HCL, including soluble IRTA [62, 63] and soluble CD22 (sCD22). The sCD22 assay may be particularly appropriate for following HCL, especially in patients with limited expression of CD25 as in HCLv. While soluble CD20 (cCD20) has been described [64, 65], this marker would be difficult to assess because it would bind to rituximab which has a long half-life. sCD22 does not bind to rituximab and may be a sensitive indicator of extent of response and predicting early relapse.

1.3.10 Simultaneous rituximab and cladribine as an outpatient

An important secondary objective is to determine if combined cladribine and rituximab are feasible to administer as an outpatient. Enrollment of non-randomized patients to begin rituximab immediately prior to cladribine may facilitate outpatient administration by obviating the time needed for randomization. Also, changing the sequence of first doses of rituximab and cladribine to rituximab first may avoid rapid thrombocytopenia, which could in some cases require inpatient treatment. A 25-patient cohort treated in nonrandomized fashion will permit >80% power to rule out a 12-16% decrease in MRD-free rate from that observed in the randomized newly diagnosed HCL patients receiving cladribine prior first dose of rituximab.

1.3.11 Relationship of this trial to current research performed in LMB

The Laboratory of Molecular Biology (LMB) is currently developing recombinant immunotoxins for treating several forms of cancer, and the most successful trials have been performed in patients with HCL [35-38]. A major and increasing focus of the lab is in studying MRD after treatment for HCL using the highly sensitive RQ-PCR assay, and this assay has already been used to study MRD after purine analog and rituximab [48]. The lab is also studying the biology of HCL through patient samples obtained and has the largest molecular database of HCL patients reported [66-68]. Patient recruitment for HCL trials has been very strong and the growing population of untreated patients seeking advice indicates that a trial earlier in the disease would also accrue well at NIH. In addition to the RQ-PCR assay in the LMB which needs to be tested after agents other than immunotoxins, the Laboratory of Pathology has excellent tools for studying HCL MRD, including flow cytometry, consensus PCR, and immunohistochemistry [46, 48]. Finally, this trial can benefit the LMB immunotoxin program by identifying a group of patients eligible in the near future for immunotoxin trials. Recombinant immunotoxin HA22 [69], an improved version of BL22, is the agent now being developed for treatment of cladribine-resistant HCL. The phase II trial of BL22 in patients with HCL showed that tumor burden affected response. For example, patients with spleens < 200 mm had a 95% overall response rate (ORR), compared to 20% (p = 0.001) in patients with larger spleens or 33% (p = 0.0007) in patients post splenectomy. These results argue that close follow-up of HCL patients after standard therapy and treatment with BL22 in early relapse may be beneficial. Thus an added benefit of this trial will be the ability to prospectively follow a large number of HCL patients after standard therapy, monitoring for early relapse. These patients may be eligible for a pivotal study of an immunotoxin for HCL.

1.3.12 Problem in randomizing patients with variant HCL (HCLv)

A CD25-negative variant of HCL has been recognized since 1980 in which patients have a poorer prognosis with standard therapy [70]. In contrast to the excellent results with initial cladribine in classic HCL, HCLv responds poorly. For example, only 4 PRs were reported in 8 with HCLv [71], 2 PRs were reported out of 6 with HCLv [72], and 1 PR was reported in 3 Japanese HCLv patients [73]. Of these 17 HCLv patients from the literature, prior purine analog treatment included pentostatin in 4 cases, no purine analog in 8 cases, and in 5 cases was not reported. No progression free survival (PFS) information was given. We have screened 14 HCLv patients for LMB protocols for whom we have adequate prior information to judge response to initial cladribine, and in all cases cladribine was the 1st therapy. Of these 14 HCLv patients, there were 1 CR and 3 PRs. In these 14 patients, PFS was 1.7-96.3 (median 5.2) months, with PFS 26.3 months for CR and 8.3, 11.5 and 96.3 months for PR. None of these responses are ongoing. Thus, out of 31 total

HCLv, patients, there were a total of 1 (3%) CR and 11 total responses (ORR 35%). With respect to prior purine analog treatment, 3 (75%) of 4 with prior pentostatin responded, versus 7 (32%) of 22 with no prior purine analog ($p=0.3$). Thus, there is no suggestion that untreated HCLv patients have a better response to cladribine alone compared to HCLv patients with 1 prior purine analog, and thus both these groups of HCLv patients should be considered together without further stratification. Several anecdotal cases have been reported where patients with HCLv have responded to rituximab [74-77]. In the past few years we have prescreened over 20 HCLv patients, many of whom are or would have been eligible for this study. Because patients looking into our salvage immunotoxin trials are heavily skewed toward the HCLv phenotype, and because many of these patients have not yet had the 2 prior courses of purine analog needed for salvage protocols, we believe it will not be difficult to enroll 20 HCLv into this protocol.

2 ELIGIBILITY ASSESSMENT AND ENROLLMENT

2.1 ELIGIBILITY CRITERIA

2.1.1 Inclusion Criteria

2.1.1.1 Evidence of HCL by flow cytometry, reviewed by the Laboratory of Pathology, NCI, including positivity for CD19, CD22, CD20, and CD11c.

2.1.1.2 BMBx consistent with HCL, reviewed by Laboratory of Pathology, NCI. BMBx may be negative in HCLv in patients with increasing peripheral blood HCLv cells and spleen size.

2.1.1.3 Treatment indicated based on demonstration of at least one of the following no more than 4 weeks from the time of enrollment, and no less than 6 months after prior purine analog and no less than 4 weeks after other prior treatment, if applicable.

- Neutropenia (ANC < 1000 cells/ μ l).
- Anemia (Hgb < 10g/dL).
- Thrombocytopenia (Plt < 100,000/ μ l).
- Absolute lymphocyte count (ALC) of >5,000 K/uL
- Symptomatic splenomegaly.
- Enlarging lymph nodes > 2cm.
- Repeated infections requiring oral or i.v. antibiotics.

Patients who have eligible blood counts within 4 weeks from enrollment will not be considered ineligible if subsequent blood counts prior to enrollment fluctuate and become ineligible up until the time of enrollment.

2.1.1.4 No prior purine analog therapy except up to 1 prior course of either cladribine or pentostatin.

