3.1.3 Definition of MRD positivity

To determine MRD rates for the primary endpoint, incidence of MRD 6 months after cladribine, the following 3 CLIA-certified MRD tests will be used:

- Blood FACS
- Bone marrow aspirate FACS
- BMBx IHC
- For the primary endpoint, patients will be considered MRD+ if any of these 3 tests are positive. MRD relapse is defined as FACS positivity or low blood counts (ANC < 1500/uL, Plt < 100,000/uL, or Hgb < 11). Patients FACS-negative in both blood and bone marrow aspirate are considered MRD-negative regardless of blood counts. MRD in the BMBx by IHC is defined as a ratio of CD20+ cells to T cells of at least 1, and most of the CD20+ cells having morphology consistent with HCL. FACS uses multicolor flow cytometry to specifically identify and quantify HCL cells based on expression of CD19, CD22, CD20, CD11c, CD103, and restricted (lambda or kappa) light chains. Blood consensus PCR is reported as clonal rearrangement present (positive) or polyclonal rearrangement pattern present (negative). While MRD generally refers to HCL detected while a patient is in CR, patients with more than minimal disease in the BMBx, who by definition are not in CR, will also be considered MRD+ by IHC. Patients not in CR due to positive BMBx may be MRD-free by blood tests. Thus, blood MRD-free survival is usually shorter than, but could be equal to or longer than disease-free survival.

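### The lymphocyte-count indication in Section 2.1.1.3 is written in K/uL, which makes it 1,000 times the evidently intended 5,000/uL and unreachable in practice

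*Combined protocol and SAP*

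**What the plan says.** Section 2.1.1.3 makes entry conditional on a treatment indication: "Treatment indicated based on demonstration of at least one of the following no more than 4 weeks from the time of enrollment". Seven indications follow: low neutrophils, low hemoglobin, low platelets, a high lymphocyte count, spleen symptoms, growing lymph nodes and recurrent infection. The lymphocyte line is "Absolute lymphocyte count (ALC) of >5,000 K/uL".

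The two neighbouring cell-count lines carry no K: "Neutropenia (ANC < 1000 cells/ μ l" and "Thrombocytopenia (Plt < 100,000/ μ l". The same holds for the cut-offs that define MRD relapse in Section 3.1.3 ("ANC < 1500/uL, Plt < 100,000/uL, or Hgb < 11") and for the neutrophil and platelet limits in Sections 5.2.4, 5.2.5 and 6.2.

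The unit K/uL appears nowhere else in the document, and no other section restates a lymphocyte threshold. Section 1.3.7 points back to 2.1.1.3 as the place where the indications for treatment are set out.

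**The concern.** A laboratory count reported in K/uL is a count in thousands. A threshold of 5,000 in that unit is five million lymphocytes per microlitre, so the number and the unit cannot both be right.

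The line is an operative one. Section 2.2.2.1 requires a CBC with differential for eligibility, so the value is to hand at screening. Section 12.2 has monitors verify that conduct complies with the protocol. Taken literally, the criterion would turn away a patient whose only indication is lymphocytosis. If that patient were enrolled on the obvious reading, the enrolment would depart from the written text. In either case staff have to reinterpret an inclusion criterion silently, and it cannot be audited as it stands.

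**Working it through.** The document makes no calculation here that could be reproduced. The check is a unit conversion, a comparison with another count in the document, and a tally of the list.

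**Inputs**

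| Input | Value | Source |
|---|---|---|
| Lymphocyte threshold as written | > 5,000 K/uL | Section 2.1.1.3 |
| Meaning of K | 1,000 cells | usual laboratory convention; not defined in the document |
| Neutrophil and platelet units in the same list | cells per uL, no multiplier | Section 2.1.1.3 |
| Count treated as a high number of circulating malignant cells | 25,000/mm3 (1 mm3 = 1 uL) | Section 1.2.6, renal events |
| Number of indications, any one sufficient | 7 | Section 2.1.1.3 |

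**Step 1. Threshold as written.** 5,000 K/uL x 1,000 cells per K = 5,000,000 cells/uL.

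**Step 2. Intended threshold.** There are two natural repairs.
- Drop the K: 5,000 cells/uL.
- Keep the K and drop the thousands: 5 K/uL = 5 x 1,000 = 5,000 cells/uL.

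Both give the same value, so the correction involves no clinical choice.

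**Step 3. Size of the error.** 5,000,000 / 5,000 = 1,000.

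**Step 4. Plausibility against the document's own benchmark.**
- As written: 5,000,000 / 25,000 = 200 times the count that Section 1.2.6 calls high.
- As intended: 5,000 / 25,000 = 0.2 times that count, which is plausible as a trigger for treatment.

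The benchmark refers to malignant cells and the criterion to all lymphocytes, so the comparison shows the order of magnitude only. A ratio of 200 leaves no doubt about the conclusion.

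**Step 5. Reach.** One of 7 indications is affected and 7 - 1 = 6 are not. The lymphocyte count does not enter the stratification (Section 2.3.2), the MRD definition (3.1.3), the response criteria for CR and PR (5.2.4, 5.2.5) or the power statements (6.1, 6.2, 6.3.1).

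**The case against.** The strongest reply is that this is a typing slip with an obvious reading. The correct unit is on the page in the lines beside it, clinical staff would not apply a five-million threshold, and the team applying the line is largely the team that wrote it. No competing reading is one that a reasonable user would adopt. Nothing in the document shows that any patient was enrolled or turned away on the lymphocyte count alone, and no inference depends on it. The mistyped creatinine-clearance unit in Section 2.1.1.9 (ml/ml) is the same kind of slip and would normally go to a copy-edit list.

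Most of this stands, and it sets the size of the point. Staff would probably read the line as 5,000/uL. Section 1.3.8 considers it "feasible to recruit all the patients using NIH as a single site", so different readings across sites are not at issue.

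It is also uncertain which patients would be exposed. Section 2.1.1.2 says "BMBx may be negative in HCLv in patients with increasing peripheral blood HCLv cells and spleen size", which suggests that circulating disease can be prominent in the variant. But the document does not say that such patients would lack every other indication, and an enlarging spleen is not the same as a symptomatic one. No estimate of affected patients can be drawn from this.

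The reply does not make the text correct. This is a numerical decision threshold in an inclusion criterion, and followed as written it gives the wrong eligibility decision for a patient whose only indication is lymphocytosis.

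**Conclusion.** The criterion is wrong as written, and the point is minor. The lymphocyte threshold is 5,000,000/uL where 5,000/uL is evidently meant, a factor of 1,000, and one of the seven sufficient indications cannot be met in practice.

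The conclusion rests on two inferences: that K means thousand, which the document does not define, and that the intended unit is the plain per-microlitre count used in the neighbouring lines. Both are safe, and the two natural corrections agree.

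The number of patients affected, if any, is not given. Design, sample size, power, significance level and endpoints are unaffected.

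**What to change.** In the next amendment, change the line in Section 2.1.1.3 to **ALC > 5,000/uL**, in the same unit as the neutrophil and platelet lines. If anyone was enrolled on the lymphocyte count alone, record that consistently against the corrected threshold. If there was no such patient, nothing further is needed. The cost is a one-line correction.

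As a separate editorial item, the same amendment can change the creatinine-clearance unit in Section 2.1.1.9 from ml/ml to ml/min.

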2.1.1.5 No prior rituximab unless HCLv patient

2.1.1.6 ECOG performance status [78] of 0-3 (see [Appendix C](#)).

2.1.1.7 Patients must be able to understand and give informed consent.

- 2.1.1.8 Women of child-bearing age and all men must use birth control of any type until at least 12 months after the last dose of therapy.
- 2.1.1.9 Creatinine \leq 1.5 or creatinine clearance \geq 60 ml/ml.
- 2.1.1.10 Bilirubin \leq 2 unless consistent with Gilbert's (total/direct $>$ 5), ALT and AST \leq 2.5 x upper limits of normal.
- 2.1.1.11 No other therapy (i.e. chemotherapy, interferon) for 4 weeks prior to study entry, or cladribine for 6 months prior to study entry.
- 2.1.1.12 Age at least 18
- 2.1.1.13 Men and women of reproductive potential must agree to use an acceptable method of birth control during treatment and for twelve months after completion of treatment.
- 2.1.1.14 Subject has provided written informed consent
- 2.1.1.15 Patients must be willing to co-enroll in the investigator's companion protocol 10-C-0066 titled "Collection of Human Samples to Study Hairy Cell and other Leukemias, and to Develop Recombinant Immunotoxins for Cancer Treatment".

2.1.2 Exclusion Criteria

- 2.1.2.1 Presence of active untreated infection
- 2.1.2.2 Uncontrolled coronary disease or NYHA class III-IV heart disease (see [Appendix D: New York Heart Association Classification](#)).
- 2.1.2.3 Known infection with HIV. Hepatitis B is allowed only if viral load is undetectable and if on anti-hepatitis B therapy like Entecavir. Hepatitis C is allowed only if viral load is undetectable, and if the patient has received curative therapy.
- 2.1.2.4 Patients with documented history of no response to cladribine, and without 50% improvement in platelets, hemoglobin or granulocytes. This exclusion does not apply to HCLv. These patients are eligible regardless of prior response to CDA.
- 2.1.2.5 Pregnant or lactating women.
- 2.1.2.6 Presence of active 2nd malignancy requiring treatment. 2nd malignancies with low activity which do not require treatment (i.e. low grade prostate cancer, basal cell or squamous cell skin cancer) do not constitute exclusions.
- 2.1.2.7 Inability to comply with study and/or follow-up procedures.
- 2.1.2.8 Presence of CNS disease, which is symptomatic.
- 2.1.2.9 At the Investigator's discretion, receipt of a live vaccine within 4 weeks prior to randomization. Efficacy and/or safety of immunization during periods of B-cell depletion have not been adequately studied. It is recommended that a patient's vaccination record and possible requirements be reviewed. Per the investigator's discretion, the patient may have any required vaccination/booster administered at least 4 weeks prior to the initiation of study treatment. Review of the patient's immunization status for the following vaccinations is recommended: tetanus; diphtheria; influenza; pneumococcal polysaccharide; *Varicella*; measles, mumps and rubella (MMR); and hepatitis B. Patients who are considered to be at high risk for hepatitis B virus (HBV) infection and for whom

the investigator has determined that immunization is indicated should complete the entire HBV vaccine series at least 4 weeks prior to participation in the study.

2.1.3 Recruitment Strategies

This protocol may be abstracted into a plain language announcement posted on NIH websites and on NIH social media platforms. Prior to distribution of any recruitment materials, such materials will be submitted to the IRB for review.

2.2 SCREENING EVALUATION

2.2.1 Screening activities performed prior to obtaining informed consent

Minimal risk activities that may be performed before the subject has signed a consent include the following:

- Email, written, in person or telephone communications with prospective subjects
- Review of existing medical records to include H&P, laboratory studies, etc.
- Review of existing MRI, x-ray, or CT images
- Review of existing photographs or videos
- Review of existing pathology specimens/reports from a specimen obtained for diagnostic purposes

A waiver of consent for these activities has been requested in Section [8.5.2](#).

